		1		2		Cycle 3 Onwards ^a	At DC		Safety ^{b,c}	Efficacy Follow-up Visits ^d	Survival	
Visit Timing/Cycle Number	-28 to -1	1		2		Cycle 3 Onwards ^a	At DC	30 Days and 90 Days After Last Dose	Q12W	Q12W	All procedures and assessments are to be performed prior to administration of study intervention unless otherwise indicated. Refer to Section 8 for visit details.	
Cycle Day		1	8	15	1	15	1					
Scheduling Window (Days)	-28 to -1		±3	±3	±3	±3	±3		+7	±7	±7	
Vital signs (resting BP, heart rate, RR, and temp) and weight	X	X		X	X	X	X	X	X			Blood pressure and pulse will be measured after the participant has been resting for 5 minutes. See Section 6.6.2.1 for management of hypertension and Section 8.3.2 for vital signs. Height measured at Screening only.
12-lead ECG	X	X			X		X	X	X			Single 12-lead ECG. Participants must be in the recumbent position for a period of 5 minutes prior to the ECG. ECG at Screening, C1D1, C2D1, D1 of every 4th cycle (12 weeks) thereafter (eg, C6, C10, C14, etc.), EOT, and Safety Follow-up. For high-risk participants (Section 8.8.3), conduct ECG monitoring every cycle. If lenvatinib is discontinued, ECGs are only required at the EOT and Safety Follow-up visits. Additional assessments may be performed if clinically indicated. At C1D1 only, an additional 2-hour post-lenvatinib dose ECG is required.

Study Period	Screening	Treatment Cycle = 21 days						EOT ^b	Posttreatment Visits			Notes
		1		2		Cycle 3 Onwards ^a	At DC		Safety ^{b,c}	Efficacy Follow-up Visits ^d	Survival	
Visit Timing/Cycle Number	-28 to -1	1		2		Cycle 3 Onwards ^a	At DC	30 Days and 90 Days After Last Dose	Q12W	Q12W	All procedures and assessments are to be performed prior to administration of study intervention unless otherwise indicated. Refer to Section 8 for visit details.	
Cycle Day		1	8	15	1	15	1					
Scheduling Window (Days)	-28 to -1		±3	±3	±3	±3	±3		+7	±7	±7	
MUGA or ECHO for LVEF assessment	X							X			Additional assessments as clinically indicated. Assessments should use the same method (MUGA or ECHO) throughout the study.	
Hematology and clinical chemistry laboratory assessment	X			X	X	X	X	X	X		Procedures/assessments should be performed within 3 days prior to administration of first dose of study intervention and prior to all subsequent scheduled visits. Every effort should be made to collect samples at the same time of day. LDH is only required at Screening.	

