13. Have adequately controlled BP, with or without antihypertensive medications, defined as BP \leq 150/90 mmHg at Screening and no change in antihypertensive medications within 1 week before Cycle 1, Day 1.

Note: Eligibility of a participant that is receiving >3 antihypertensive medications prior to study entry will require Sponsor approval

14. Have adequate organ function as defined in [Table 2](#). Specimens must be collected within 3 days prior to the start of study intervention.

Table 2 Adequate Organ Function Laboratory Values

System	Laboratory Value
Hematological	
Absolute neutrophil count (ANC)	$\geq 1500/\mu\text{L}$
Platelets	$\geq 100\,000/\mu\text{L}$
Hemoglobin	$\geq 9.0\text{ g/dL}$ or $\geq 5.6\text{ mmol/L}^{\text{a}}$
Renal	
Creatinine OR Measured or calculated ^b creatinine clearance (GFR can also be used in place of creatinine or CrCl)	$\leq 1.5 \times \text{ULN}$ OR $\geq 30\text{ mL/min}$ for participant with creatinine levels $> 1.5 \times \text{institutional ULN}$
Hepatic	
Total bilirubin	$\leq 1.5 \times \text{ULN}$ OR direct bilirubin $\leq \text{ULN}$ for participants with total bilirubin levels $> 1.5 \times \text{ULN}$ except for unconjugated hyperbilirubinemia of Gilbert's syndrome.
AST (SGOT) and ALT (SGPT), and ALP	$\leq 2.5 \times \text{ULN}$ ($\leq 5 \times \text{ULN}$ for participants with liver metastases) ^c
Coagulation	
International normalized ratio (INR) OR prothrombin time (PT) Activated partial thromboplastin time (aPTT)/PTT	$\leq 1.5 \times \text{ULN}$ unless participant is receiving anticoagulant therapy as long as PT or PTT is within therapeutic range of intended use of anticoagulants
Abbreviations: ALT (SGPT) = alanine aminotransferase (serum glutamic pyruvic transaminase); AST (SGOT) = aspartate aminotransferase (serum glutamic oxaloacetic transaminase); ALP = alkaline phosphatase; CrCl = creatinine clearance; GFR = glomerular filtration rate; ULN = upper limit of normal.	
a Criteria must be met without erythropoietin dependency and without packed red blood cell (pRBC) transfusion within last 2 weeks.	
b Creatinine clearance (CrCl) should be calculated per institutional standard.	

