6.6.3 Dose Modifications for Overlapping Toxicities

Based on the known toxicity profiles of pembrolizumab and lenvatinib, certain treatment-related AEs are uniquely associated with one drug versus the other. For example, hypertension, arterial thrombotic events, proteinuria, and hemorrhagic events are known risks for lenvatinib treatment, while immune-related AEs are risks for pembrolizumab treatment. However, certain AEs, such as diarrhea, hypothyroidism, and liver enzyme elevation, may be initially considered attributable to either study drug. Therefore, evaluation of attribution is important for determining the study drug most likely related to the AE, or an alternative etiology, and subsequently proper clinical management. The following aspects should be considered:

1. Timing of AE onset

Since lenvatinib is dosed daily and continuously due to a relatively short half-life (~28 hours), and pembrolizumab is dosed Q3W due to a long half-life, lenvatinib can be interrupted to assess whether an AE improves/resolves with dechallenge (ie, interruption of treatment) based on the following 2 scenarios:

- If an AE is identified during a treatment cycle (ie, between 2 pembrolizumab doses), only lenvatinib dose interruption is needed.
- If an AE is identified at the beginning of a treatment cycle, lenvatinib can be interrupted and dosing of pembrolizumab should be held.

If the participant recovers from an AE in response to lenvatinib interruption (ie, positive dechallenge), the event is more likely to be related to lenvatinib. Otherwise, after excluding other alternative explanations, an immune-related AE should be considered.

2. Severity of AE

If an AE is suspected to be treatment related and is severe/life threatening at the time of onset or is rapidly worsened, action including interrupting both drugs and initiating treatment with a corticosteroid (with exception of hypothyroidism, T1DM) and other supportive care should be taken promptly.

3. Participants receiving the combination therapy (pembrolizumab + lenvatinib) must discontinue study intervention if any of the following occur:
 - ALT or AST $>5 \times$ ULN for more than 2 weeks
Pembrolizumab will have already been permanently discontinued per Table 4, but lenvatinib may be administered at a reduced dose by the time this criterion is met and must be permanently discontinued immediately.
 - ALT or AST $>3 \times$ ULN and (TBL $>2 \times$ ULN or INR >1.5)

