Although Table 4 advises pembrolizumab to be withheld (interrupted), and Table 6 advises lenvatinib to have no dose modification or a reduction, if this criterion is met, both drugs must be permanently discontinued immediately.

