7 DISCONTINUATION OF STUDY INTERVENTION AND PARTICIPANT WITHDRAWAL

7.1 Discontinuation of Study Intervention

Discontinuation of study intervention does not represent withdrawal from the study.

As certain data on clinical events beyond study intervention discontinuation may be important to the study, they must be collected through the participant's last scheduled follow-up, even if the participant has discontinued study intervention. Therefore, all participants who discontinue study intervention prior to completion of the protocol-specified treatment period will still continue to participate in the study as specified in Section 1.3 and Section 8.10.3.

Participants may discontinue study intervention at any time for any reason or be discontinued from the study intervention at the discretion of the investigator should any untoward effect occur. In addition, a participant may be discontinued from study intervention by the investigator or the Sponsor if study intervention is inappropriate, the study plan is violated, or for administrative and/or other safety reasons. Specific details regarding procedures to be performed at study intervention discontinuation are provided in Section 8.1.9.

A participant must be discontinued from study intervention but continue to be monitored in the study for any of the following reasons:

- The participant or participant's legally acceptable representative requests to discontinue study intervention.
- The participant has a medical condition or personal circumstance, which, in the opinion of the investigator and/or Sponsor, placed the participant at unnecessary risk from continued administration of study intervention.
- The participant has a confirmed positive serum pregnancy test.
- Progressive disease as verified by investigator.

Note: Participants will be permitted to continue treatment beyond confirmed RECIST 1.1-defined progression if investigator-assessed clinical stability is observed, and the participant is tolerating study intervention (Section 8). Treatment beyond progressive disease per iRECIST may be permitted following Sponsor consultation and approval.

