8.3.5.1 Hematology and Clinical Chemistry

Hematology and clinical chemistry assessments will be performed within 3 days prior to administration of first dose of study intervention and prior to all subsequent scheduled visits. The results must be reviewed prior to administration of study therapy. Electrolytes such as potassium, calcium, and magnesium should be monitored and abnormalities, when considered clinically significant, should be corrected in all participants before starting treatment.

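### For participants with liver metastases, Table 2 admits some ALT/AST and bilirubin values that already meet the permanent hepatic stopping criterion in Sections 6.6.3 and 7.1

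*Combined protocol and SAP*

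**What the plan says.** **Entry (Section 5.1, Table 2).** AST and ALT must be at most 2.5 x ULN, relaxed to 5 x ULN "for participants with liver metastases". Total bilirubin must be at most 1.5 x ULN. Above that, direct bilirubin must be at most ULN, with a clause reading "except for unconjugated hyperbilirubinemia of" Gilbert's syndrome. The direct-bilirubin branch sets no upper limit on total bilirubin.

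**Stopping (Section 6.6.3, item 3).** "Participants receiving the combination therapy (pembrolizumab + lenvatinib) must discontinue study intervention if any of the following occur". The second event is ALT or AST >3 x ULN together with total bilirubin >2 x ULN or INR >1.5. The text acknowledges that Tables 4 and 6 would be milder, then says "if this criterion is met, both drugs must be permanently discontinued immediately". Section 7.1 repeats the criterion in a list headed "A participant must be discontinued from study intervention but continue to be monitored in the study for any of the following reasons".

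**Timing.** For hematology and chemistry the Schedule of Activities (Section 1.3) says: "Procedures/assessments should be performed within 3 days prior to administration of first dose of study intervention and prior to all subsequent scheduled visits". The first on-treatment chemistry is Cycle 1 Day 15. Section 8.3.5.1 adds: "The results must be reviewed prior to administration of study therapy".

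**Analysis.** Participants who discontinue are not replaced (Section 5.5). Everyone allocated who received at least one dose is in the APaT population, which is the ORR denominator (Sections 9.5.1 and 9.6.1.1).

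**The concern.** The entry limits and the stopping limits were not aligned for this one group. The protocol admits a participant whose screening values already satisfy a mandatory, permanent stopping criterion. Because the criterion addresses participants receiving the combination, it can first bite only after dosing has begun.

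Two outcomes are possible and neither is good. If the rule is applied literally, a participant is exposed to both drugs and then barred from them although nothing has changed. If a site reads the rule as covering only new events, it continues treatment. A liver-safety rule could then be applied differently from site to site. The stake is mainly clarity of conduct for a small eligible group. The effect on the primary estimate is slight.

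**Working it through.** **1. The two rules as logical conditions** (multiples of ULN; bilirubin limb of the stopping criterion only)

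- Eligible: ALT <=5 with liver metastases, or <=2.5 without; and (total bilirubin <=1.5, or direct bilirubin <=1).
- Stop: ALT >3 and total bilirubin >2.

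Both hold when liver metastases are present, 3 < ALT <= 5, total bilirubin >2 and direct bilirubin <=1.

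**2. Single cases, all with liver metastases**

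| ALT | Total bilirubin | Direct bilirubin | Eligible | Meets stop |
|---|---|---|---|---|
| 4 | 2.5 | 0.9 | yes | yes |
| 4 | 1.4 | 1.2 | yes | no |

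The second row shows that only some admitted values conflict.

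**3. Grid check.** ALT 2 to 5 by 0.5 (7 values); total bilirubin 1 to 3 by 0.5 (5 values); direct bilirubin <=ULN yes or no.

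- Bilirubin combinations admitted: totals of 1 and 1.5 with either direct status (4), plus 2, 2.5 and 3 with direct <=ULN (3), giving 7.
- With liver metastases: 7 x 7 = 49 eligible cells. Overlap: ALT 3.5, 4, 4.5 and 5 (4) x total bilirubin 2.5 and 3 (2) = 8 cells.
- Without liver metastases: ALT 2 and 2.5 only, so 2 x 7 = 14 eligible cells and 0 overlap.

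So 8 of 63 eligible cells conflict, all with liver metastases. Cells are combinations of values, not prevalences.

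**4. The other hepatic criterion.** ALT or AST >5 x ULN for more than 2 weeks cannot be met at entry, because the ceiling is 5 x ULN.

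**5. Exposure before the literal stop.** One pembrolizumab dose, and lenvatinib on Days 1 to 14 = 14 doses (11 to 17 with the 3-day visit window). The first scan is due 63 +/- 7 days after allocation (Section 8.2.1.2), that is Day 56 to 70. Taking first dose and allocation on the same day (assumption), 56 - 14 = 42 and 70 - 14 = 56, so the stop falls 6 to 8 weeks before that scan.

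**6. Effect on ORR.** Table 13 gives 30/100 = 30% (21.2%, 40.0%), and the Clopper-Pearson calculation reproduces it. One lost responder gives 29/100 = 29% (20.4%, 38.9%); three give 27/100 = 27% (18.6%, 36.8%). The ceiling is therefore 1/100 = 1 point per affected participant. As an illustration only, applying Table 13's response rates of 20% to 55% and assuming no response after stopping, the expected loss is 1 x 0.20 to 1 x 0.55 = 0.20 to 0.55 points each.

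**The case against.** The strongest reply is that the rule concerns events that arise on treatment. It uses the verb *occur*, and it sits in a section about attributing treatment-related toxicity and timing of onset. Its own rider refers to Tables 4 and 6, which deal with immune-related and treatment-related events. Section 6.5.4 ties the management guidance to events judged drug-related. Appendix 3 does not count fluctuation in a condition present at study start as an adverse event if it does not worsen. Exclusion criterion 24 also lets the investigator refuse a participant whose laboratory abnormality could interfere with full participation.

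Part of this stands. A new-onset reading is reasonable, so a reader might infer, but cannot conclude from the text, that every such participant will be stopped at Cycle 1 Day 15. The opposite certainty is not supported either. The trigger is a laboratory threshold, not an adverse event. Item 3 of Section 6.6.3 carries no attribution or baseline condition. Section 7.1 offers Sponsor discretion for treatment beyond iRECIST progression but none here. Where the protocol wants an adjusted baseline it writes one, as for weight loss in Table 6, footnote d. Exclusion 24 is discretionary, so it narrows the gap without closing it.

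A reader might also infer that the INR limb has the same defect. On paper the values can coincide, because Table 2 lifts the INR limit "unless participant is receiving anticoagulant therapy as long as PT or PTT is within therapeutic range of intended use of anticoagulants". But PT/INR is scheduled at screening only, so no scheduled on-treatment test would trigger that limb. Without anticoagulation, an overlap needs a laboratory ULN for INR above 1.0, which the documents do not give. The waiver is explicit, and excluding these people would override it. It would also leave an entrant at ALT 2.9 x ULN and INR 2.5 to be stopped at ALT 3.1 x ULN. Whether to exclude anticoagulated participants or exempt them from the INR limb is a clinical choice.

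**Conclusion.** The conflict holds for the bilirubin limb. It is confined to participants with liver metastases, ALT or AST above 3 and up to 5 x ULN, total bilirubin above 2 x ULN, and direct bilirubin at or below ULN. The text does not settle whether unchanged entry values count, so the practical defect is either a stop on entry values or inconsistent application.

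The size is minor. The documents give no frequency for this combination, and needing all four features together makes it probably very small. If 1 to 3 participants were affected (assumption), the ceiling on ORR is 1 to 3 points. A reader might infer that the primary result is at risk, but the documents do not support that. There is no hypothesis test. The intervals in step 6 overlap almost entirely. Imaging continues after discontinuation without progression (Section 8.2.1.3), so a later response could still count. The expected-loss figures borrow Table 13's response rates for a subgroup the plan does not describe and should be read only as scale.

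**What to change.** Leave the stopping rule in Sections 6.6.3 and 7.1 unchanged. Add one line to Table 2: *Participants with screening ALT or AST >3 x ULN and total bilirubin >2 x ULN are not eligible.* In the grid this removes the 8 conflicting cells and keeps the other 55, as it must by construction.

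No new test is needed: ALT, AST and total bilirubin are already measured at screening. The cost is a few screen failures, for example someone with Gilbert's syndrome and liver metastases whose values fall in this range. They would not have been dosed, so they stay outside APaT. They may be rescreened (Section 8.10.1.1), with Sponsor agreement for repeat laboratory tests (Section 8.10.1). The line does not help a participant who enters just under the ALT threshold and then crosses it, but that stop would follow a real on-treatment change.

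The alternative is to limit the stopping rule to new or worsening values. That would also resolve the conflict, but it changes a liver-safety rule and so needs a clinical decision.

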6.6.4 Other Allowed Dose Interruptions for Lenvatinib and Pembrolizumab

If the participant is receiving treatment with lenvatinib and requires surgery during the study, the stop time and restart time of lenvatinib should be as follows:

- For minor procedures: stop lenvatinib at least 2 days before the procedure and restart it at least 2 days after, once there is evidence of adequate healing and no risk of bleeding.
- For major procedures: stop lenvatinib at least 1 week (5 half-lives) prior to surgery and then restart it at least 1 week after, once there is evidence of adequate healing and no risk of bleeding.

Pembrolizumab may be interrupted for situations other than treatment-related AEs such as medical/surgical events or logistical reasons not related to study therapy. Participants should be placed back on study therapy within 3 weeks of the scheduled interruption, unless otherwise discussed with the Sponsor. The reason for interruption should be documented in the participant's study record.

6.7 Intervention After the End of the Study

There is no study-specified intervention following the end of the study.

6.8 Clinical Supplies Disclosure

This study is open-label; therefore, the participant, the study site personnel, the Sponsor, and/or designee are not blinded. Study intervention is included in the label text; random code/disclosure envelopes or lists are not provided.

7 DISCONTINUATION OF STUDY INTERVENTION AND PARTICIPANT WITHDRAWAL

7.1 Discontinuation of Study Intervention

Discontinuation of study intervention does not represent withdrawal from the study.

As certain data on clinical events beyond study intervention discontinuation may be important to the study, they must be collected through the participant's last scheduled follow-up, even if the participant has discontinued study intervention. Therefore, all participants who discontinue study intervention prior to completion of the protocol-specified treatment period will still continue to participate in the study as specified in Section 1.3 and Section 8.10.3.

Participants may discontinue study intervention at any time for any reason or be discontinued from the study intervention at the discretion of the investigator should any untoward effect occur. In addition, a participant may be discontinued from study intervention by the investigator or the Sponsor if study intervention is inappropriate, the study plan is violated, or for administrative and/or other safety reasons. Specific details regarding procedures to be performed at study intervention discontinuation are provided in Section 8.1.9.

A participant must be discontinued from study intervention but continue to be monitored in the study for any of the following reasons:

- The participant or participant's legally acceptable representative requests to discontinue study intervention.
- The participant has a medical condition or personal circumstance, which, in the opinion of the investigator and/or Sponsor, placed the participant at unnecessary risk from continued administration of study intervention.
- The participant has a confirmed positive serum pregnancy test.
- Progressive disease as verified by investigator.

Note: Participants will be permitted to continue treatment beyond confirmed RECIST 1.1-defined progression if investigator-assessed clinical stability is observed, and the participant is tolerating study intervention (Section 8). Treatment beyond progressive disease per iRECIST may be permitted following Sponsor consultation and approval.

- Any progression or recurrence of any malignancy, or any occurrence of another malignancy that requires active treatment. Exceptions to secondary malignancy include basal cell carcinoma of the skin, squamous cell carcinoma of the skin, new non-ulcerated primary melanoma <1 mm in depth with no nodal involvement, or carcinoma in situ (eg, breast carcinoma, cervical cancer in situ) that have undergone potentially curative therapy. Exceptions should be discussed with the Sponsor prior to continuing therapy or remaining in follow-up.
- Recurrent Grade 2 pneumonitis and other AEs that may require treatment discontinuation per Section 6.6 (Dose Modification).

- Completion of 35 treatments (approximately 2 years) with pembrolizumab.
Note: Participants may receive lenvatinib monotherapy until disease progression or unacceptable toxicity.
- Grade 3 thromboembolic events require permanent discontinuation of lenvatinib.
- Participants receiving the combination therapy (pembrolizumab + lenvatinib) must discontinue study intervention if any of the following occur:
 - ALT or AST $>5 \times$ ULN for more than 2 weeks
Pembrolizumab will have already been permanently discontinued per [Table 4](#), but lenvatinib may be administered at a reduced dose by the time this criterion is met and must be permanently discontinued immediately.
 - ALT or AST $>3 \times$ ULN and (TBL $>2 \times$ ULN or INR >1.5)
Although [Table 4](#) advises pembrolizumab to be withheld (interrupted), and [Table 6](#) advises lenvatinib to have no dose modification or a reduction, if this criterion is met, both drugs must be permanently discontinued immediately.

A participant may be discontinued from study intervention but continue to be monitored in the study for the following reason:

- Discontinuation of study intervention with pembrolizumab and lenvatinib may be considered for participants who have attained a confirmed CR and have been treated for at least 24 weeks, receiving at least 2 doses of pembrolizumab beyond the date when the initial CR was declared.

Note: The number of treatments is calculated starting with the first dose of pembrolizumab.

